Research Protocol

Project Title

Peak cardiac output determined using inert gas rebreathing: A comparison of two exercise protocols

Principal Investigator

[name].
Professor
Department of Kinesiology
McMaster University

Student Investigator

[name], M.Sc.
Ph.D. Candidate
Department of Kinesiology
McMaster University

Background and rationale

The “gold standard” methods for determining cardiac output (Q) are the direct Fick and thermodilution techniques (1). Both are highly technical and very invasive, requiring arterial catheterization. Q can be estimated non-invasively using inert gas rebreathing (IGR). The IGR method involves taking 5-6 breaths from a closed-circuit rebreathing bag that contains a mixture of oxygen and inert gases. The Innocor (COSMED, Italy) is a popular commercially available device that uses oxygen (94%), an inert blood soluble gas (nitrous oxide, 5%), and an inert blood insoluble gas (sulfur hexafluoride, 1%) (2). Photoacoustic gas analyzers monitor the expired air and measure the disappearance rate of the blood soluble gas relative to the blood insoluble gas over the course of the rebreathing period to estimate Q.

IGR-derived Q using the Innocor correlates well with the direct Fick ($r=0.95$) and thermodilution ($r=0.94$) methods during maximal exercise (3, 4). A recent review comprising 10 clinical studies found that the correlation between IGR and the Fick method was higher than the correlation between the thermodilution and Fick method during submaximal steady state exercise (IGR vs Fick: $r=0.84$ [95% CI 0.74-0.90]; thermodilution vs Fick: $r=0.73$ [95% CI 0.61-0.82]), and that IGR demonstrated good Bland-Altman Limits of Agreement with the Fick method (1).

Moreover, IGR had a higher reliability than the thermodilution method (IGR typical error [TE]=7.2%; thermodilution TE=13.2%) (1). Further, the Fick and thermodilution methods yield greater inter-subject variability estimated by standard deviation during maximal exercise compared to IGR (Fick standard deviation [SD]=3.9 L/min; thermodilution SD=3.8 /min; IGR SD=2.2 L/min) (5). Therefore, IGR provides a noninvasive estimation of peak cardiac output (Q_{peak}) that is accurate and potentially more reliable than invasive measures. The latter may be

owing to the fact that the relative simplicity of the IGR method reduces assessor variability, and it is less susceptible to excessive movement during exercise.

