A challenge inherent to the IGR technique for estimating Q_{peak} is the selection of an appropriate exercise protocol and deciding when to initiate the rebreathing procedure. The rebreathing requires a measurement period of ~ 10 s during “maximal” exercise or as close to this point as possible, while ensuring the participant can maintain the exercise load throughout the entire rebreathing period. There is no consensus regarding the optimal exercise protocol to measure IGR-derived Q_{peak} . One commonly-used protocol involves an incremental (step) exercise test with rebreathing initiated when the participant reaches a heart rate (HR) that is within 5 bpm of a previously determined peak value (the Q_{step} protocol) (6). Iterations of this protocol involve initiating rebreathing when the participant self-reports that they are ~ 30 s from exhaustion, or when the workload corresponds to the peak power output from a previously completed step test to exhaustion (7), as opposed to when a pre-determined HR is reached. The TE of step test determinations of Q_{peak} have been reported to be $\sim 7\%$ (1, 8).

We recently developed an exercise protocol for the IGR-derived estimation of Q_{peak} (the Q_{CL} protocol) (9) that was modelled after tests of $VO_{2\text{peak}}$ that involve a “verification phase” (10, 11). It involved a ramp exercise test to elicit $VO_{2\text{peak}}$, followed by a constant load exercise phase after a brief recovery interval, and the TE was 4.7% (9). The constant load phase was performed at $\sim 90\%$ of the workload that elicited $VO_{2\text{peak}}$, with rebreathing to estimate Q_{peak} initiated after 2 minutes. This protocol was developed based on previous research studies that found that constant load exercise performed at $>85\%$ W_{peak} can elicit comparable VO_2 values, and HR values that are within $\sim 5\%$ of those obtained at the end of a ramp $VO_{2\text{peak}}$ test (9–12). The use of a constant load phase to measure Q_{peak} allows for the measurement of this parameter during the same test as used

to determine $VO_{2\text{peak}}$, in contrast to the Q_{step} protocol which must be performed on a different day. This may be convenient for training studies (i.e., reducing the need for two tests). No study has compared Q_{peak} between the Q_{CL} and Q_{step} protocols, and no study has assessed the reliability of the Q_{CL} and Q_{step} protocols for determining Q_{peak} within the same group of participants.

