$VO_{2\text{peak}}$ between the $VO_{2\text{peak}}$ test, the $VO_{2\text{CL}}$ protocol and the $VO_{2\text{step}}$ protocol.

$VO_{2\text{peak}}$ between the Q_{CL} vs $VO_{2\text{CL}}$ tests and the Q_{step} vs $VO_{2\text{step}}$ tests.

$VO_{2\text{peak}}$ tests

For the determination of $VO_{2\text{peak}}$, participants will perform a progressive exercise test to maximal voluntary exertion using an electromagnetically braked cycle ergometer (Lode Excalibur Sport V2.0, Groningen, The Netherlands). Following a 3 min warm-up at a fixed workload of 50 W, a ramp protocol will be applied with a linear workload increase of 1 W every 2 s (30 W/min). The

precise protocol will be standardized for a given participant and intend to achieve a ramp duration of ~10 min (range: 5-15 min). Pedaling cadence will be chosen by the participant and will be required to be ≥ 60 rpm. A 3-min recovery phase will be performed at 50 W. Gas exchange and ventilatory variables will be continuously determined using a metabolic cart (Quark CPET metabolic cart, COSMED, Italy). Data will be averaged over 10-s intervals and $VO_{2\text{peak}}$ will be defined as the highest 30-s average over three consecutive intervals. Heart rate will be recorded continuously (Polar A3, Finland) and HR_{peak} will be defined as the highest 2-s average. Data-based cutoffs for age-stratified secondary exhaustion criteria based on peak respiratory exchange ratio and age-predicted maximal heart rate (16) will be used to verify that the test involved maximal effort. The highest $VO_{2\text{peak}}$, HR_{peak} , and W_{peak} between the baseline and verification tests will be regarded as the ‘true’ peak.

Q_{CL} protocol

This protocol involves a ramp exercise test to exhaustion, followed by a constant work rate test that is initiated after 10 minutes of active recovery (Figure 3). The ramp phase uses the same protocol as the $VO_{2\text{peak}}$ test (described above). The constant work rate phase will begin with a 1-minute warmup at 50 W. The warmup will be followed by an immediate increase to an intensity equivalent to 90% of the W_{peak} elicited during the baseline ramp $VO_{2\text{peak}}$ test (90% W_{peak}). HR (Polar A3, Finland) and VO_2 (Innocor, COSMED, Italy) will be monitored continuously throughout the test. The rebreathing procedure to measure Q_{peak} (Innocor, COSMED, Italy) will be initiated after 2 minutes of cycling at 90% W_{peak} .

[figure not shown]

Figure 3: Q_{CL} protocol.

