Q_{step} protocol

This test is modelled after an incremental exercise protocol that has commonly been used to assess Q_{peak} (6, 15, 17) including to assess potential changes in Q_{peak} after an exercise intervention (15). The test will begin with a 3-minute warm-up at 50 W and workload will subsequently be increased by 30 W every 1 minute (Figure 4). HR (Polar A3, Finland) and VO_2 (Innocor, COSMED, Italy) will be monitored continuously throughout the test. The rebreathing procedure to measure Q_{peak} (Innocor, COSMED, Italy) will be initiated when the participant reaches a HR that is within 5 bpm of their previously determined HR_{peak} obtained from baseline VO_{2peak} testing (visit #1 or 3 from Figure 2). W_{peak} will be calculated as $W_{peak} = W_{completed} + 30 \times (t/60)$ where $W_{completed}$ is the last completed workload and t is the time in s maintained during the final workload.

[figure not shown]

Figure 4: Q_{step} protocol.

VO_{2CL} protocol

The VO_{2CL} protocol will be identical to the Q_{CL} protocol (Figure 3), except VO_2 will be monitored continuously using the same metabolic cart as the $VO_{2\text{peak}}$ test (Quark CPET metabolic cart, COSMED, Italy), and Q_{peak} will not be assessed. The constant load $90\% W_{\text{peak}}$ phase will be 2 min and 15 s in duration; the final 15 s is added to account for the approximate time it would take for the IGR to occur.

VO_{2step} protocol

The VO_{2step} protocol will be identical to the Q_{step} protocol (Figure 4), except VO₂ will be monitored continuously using the same metabolic cart as the VO_{2peak} test (Quark CPET metabolic cart, COSMED, Italy), and Q_{peak} will not be assessed. Participants will continue cycling for an additional 15 s after reaching a HR that is within 5 bpm of HR_{peak} to account for the approximate time it would take for the IGR to occur.

Statistical analysis

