| Is the $VO_{2\text{peak}}$ measured from the Innocor noninferior to the Quark metabolic cart? | $VO_{2\text{peak}}$ from the Innocor will be inferior to the Quark metabolic cart. | Measure $VO_{2\text{peak}}$ during identical tests using the Innocor and the Quark metabolic cart (i.e., Q_{CL} vs $VO_{2\text{CL}}$ and Q_{step} vs $VO_{2\text{step}}$). | Calculate 95% CIs for the mean difference in $VO_{2\text{peak}}$ between Q_{CL} vs $VO_{2\text{CL}}$ and Q_{step} vs $VO_{2\text{step}}$. | Q_{CL} is noninferior to $VO_{2\text{CL}}$, and Q_{step} is noninferior to $VO_{2\text{step}}$ if the lower bound of the CI is within a margin of |

| | | | | |
|---|--|--|--|--|
| | | | | noninferiority of 0.2 L/min. |
| Do the experimental tests elicit VO_{2peak} that is noninferior to the VO_{2peak} test? | VO_{2peak} during the experimental tests will be noninferior to the VO_{2peak} test. | Measure VO_{2peak} during the VO_{2CL} , VO_{2step} , and baseline VO_{2peak} tests. | Calculate 95% CIs for the mean difference in VO_{2peak} between VO_{2CL} vs the baseline VO_{2peak} test and VO_{2step} vs the baseline VO_{2peak} test. | VO_{2CL} and VO_{2step} are noninferior to the baseline VO_{2peak} test if the lower bound of their respective CIs are within a margin of noninferiority of 0.2 L/min. |

Acknowledgments

We thank our colleagues who have provided input on the development of this proposal including those whose substantive contributions will be recognized with authorship on the resulting manuscript.

References

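### The Q_step and VO2_step tests match exercise time but not the usable VO2 window, which tilts the device comparison towards a lower Innocor value

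*Protocol*

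**What the plan says.** Secondary objective 3 (Protocol, Objectives) asks whether Innocor VO2 is lower than that of the metabolic cart. The Summary of analysis plan hypothesises that it is. That row plans to "Measure $VO_{2\text{peak}}$ during identical tests using the Innocor and the Quark metabolic cart", pairing Q_CL with VO2_CL and Q_step with VO2_step, and judges the lower bound of the 95% CI against 0.2 L/min.

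In Q_step, rebreathing starts when heart rate comes within 5 bpm of its known peak. In Q_CL it starts after 2 minutes at 90% W_peak. Background and rationale describes it: "The IGR method involves taking 5-6 breaths from a closed-circuit rebreathing bag that contains a mixture of oxygen and inert gases".

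The Quark versions run past those instants. For VO2_step: "Participants will continue cycling for an additional 15 s after reaching a HR that is within 5 bpm of HR_{peak". For VO2_CL, the constant-load phase lasts 2 min 15 s, and "the final 15 s is added to account for the approximate time it would take for the IGR to occur".

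The only definition of VO2peak stands under VO2peak tests: the "highest 30-s average over three consecutive intervals" of 10-s data. The Q_CL and Q_step sections say that Innocor VO2 is monitored throughout. They do not say how readings during rebreathing are treated.

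**The concern.** The added 15 s equalises time on the ergometer. It does not equalise the time over which each device can read VO2 from ordinary breathing. On the Quark those seconds are normal data. On the Innocor the participant is on the bag. A rule that picks the highest 30 s will pick the latest window while VO2 is climbing, and in the step test the load climbs until the test ends. The Quark's best window can therefore sit up to 15 s further into the exercise than the Innocor's.

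The error has one direction, and it is the hypothesised one. A difference in timing could be reported as a difference between devices.

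**Working it through.** **The plan's own figure.** The sample size of 34 (two-tailed paired t-test, d_z = 0.5, alpha 0.05) reproduces: exact power at n=34 is 0.808. It was set for Q_peak. The protocol gives no power for the device comparison, so 34 serves below only as n.

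**Inputs from the protocol.** Step rate 30 W per minute; 15 s allowance; margin 0.2 L/min on the lower 95% limit; n=34. Rebreathing is given elsewhere as shorter than 15 s: "The rebreathing requires a measurement period of ~ 10 s".

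**Assumptions not in the documents.** VO2 gain 9–11 mL/min per W; SD of paired differences 0.2–0.3 L/min; VO2 time constant 25–45 s; W_peak 250–350 W. As a check on the SD, the protocol expects a typical error of about 5% for VO2peak. Then SD = 0.05 × √2 × mean, which is 0.177 at an assumed mean of 2.5 L/min and 0.283 at 4.0.

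**Shift in the step pair.**
- 15 s: 30 W/min × 0.25 min = 7.5 W; × 9–11 mL/min per W = 67.5–82.5 mL/min, or 34–41% of the margin.
- 10 s (only the rebreathing itself is lost to the Innocor): 5 W × 9–11 = 45–55 mL/min.
- A first-order response to the actual one-minute steps, with the best 30 s ending at the trigger or 15 s later, gives the same averages: 0.067–0.082 L/min. Single values run from 0.039 to 0.117, depending on where in a step the trigger falls.
- If VO2 has plateaued, the shift shrinks towards zero.

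**Effect on the conclusions when the devices agree.** SE = SD/√34 and t(0.975, 33) = 2.035. The probability of a CI wholly below zero is the upper tail of a noncentral t beyond 2.035 with noncentrality shift/SE. The probability of meeting the margin uses (0.2 − shift)/SE. Example with SD 0.25: SE = 0.0429; 0.075/0.0429 = 1.75 gives 0.40; 0.125/0.0429 = 2.91 gives 0.81.

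| SD (L/min) | Shift (L/min) | CI wholly below 0 | Margin met |
|---|---|---|---|
| 0.20 | 0 | 0.025 | 1.00 |
| 0.25 | 0 | 0.025 | 0.995 |
| 0.30 | 0 | 0.025 | 0.965 |
| 0.20 | 0.05 | 0.29 | 0.99 |
| 0.25 | 0.05 | 0.20 | 0.92 |
| 0.30 | 0.05 | 0.15 | 0.81 |
| 0.20 | 0.075 | 0.56 | 0.94 |
| 0.25 | 0.075 | 0.40 | 0.81 |
| 0.30 | 0.075 | 0.29 | 0.65 |

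With the SD from the 5% typical error (0.177–0.283), a shift of 0.075 gives 0.67–0.32 for a CI wholly below zero and 0.98–0.71 for meeting the margin.

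**Constant-load pair.** Both Q_CL and VO2_CL contain a ramp to exhaustion. In the same first-order model, with 27 combinations of W_peak, gain and time constant, the ramp's best 30 s exceeded the constant-load best 30 s every time, even with the added 15 s. The artefact is then zero. If the comparison is restricted to the constant-load phase, the shift is 0.01–0.08 L/min. The protocol does not say which phase is meant.

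**The case against.** The 15 s is deliberate. It stands in for the rebreathing time, so the exercise performed is the same in both tests. A reader might infer that the Quark tests contain extra exercise; they do not. This point stands in full, and the mismatch concerns only what each device can measure.

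The protocol also calls Innocor monitoring continuous, never says that VO2 is lost during rebreathing, never says that the last 15 s of Quark data enter the device comparison, and attaches the 30-s rule only to the VO2peak tests. Averaging windows are often settled in a statistical analysis plan. So the bias is conditional. Still, the loss of ordinary VO2 on a closed bag of oxygen and inert gases is a sound inference, and bag readings, if kept, would not be comparable with open breathing. The protocol itself fixes the 15 s, labels the tests identical and offers a single VO2peak rule. Applied as written, that rule produces the bias.

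A reader might also infer that both pairs are biased. The documents do not support that for constant load, where the load is fixed and a ramp is recorded on either device.

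Finally, a reader might infer that noninferiority would usually be lost. At SD 0.25, the chance of meeting the margin does fall from about 93% to 40%, but only after adding a true device deficit of 0.05 L/min, for which the documents give no figure. The timing shift alone takes it from about 99.5% to 81%.

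**Conclusion.** The concern holds for the step pair. Exercise time is matched and the usable VO2 window is not, so the comparison leans towards the hypothesised lower Innocor value by about 0.07–0.08 L/min while VO2 is rising (about 0.05 if only some 10 s are lost, less on a plateau). On its own the shift stays below the 0.2 L/min margin. It therefore distorts the question whether the Innocor is lower more than it forces failure of noninferiority: a false finding of lower has probability 29–56% (15–29% at a shift of 0.05) against a nominal 2.5%.

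This rests on the assumed gain and SD, on no ordinary Innocor reading during rebreathing, and on use of the last 15 s of Quark data. For constant load the effect is nil if the ramp supplies the peak. Only a secondary objective is touched; Q_peak and its reliability are not.

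**What to change.** For the Innocor versus Quark comparison only, state that:
- Quark data after the rebreathing-equivalent instant are excluded (the heart-rate trigger in VO2_step; 2:00 at 90% W_peak in VO2_CL if the constant-load phase is used).
- Innocor data are excluded from the start of rebreathing.
- The same highest-30-s rule applies to both devices over the matched window. This keeps the peak definition and does not replace it with a fixed end-window.
- The phase of the constant-load tests that supplies VO2peak (ramp or constant load) is named.

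Keep the full 15 s for the separate comparison with the baseline VO2peak test. With matched windows the timing shift is zero. The cost is a sentence or two of analysis text; the recordings are already planned, and neither the tests nor the visits change.

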Objectives

Primary objective

To test whether the Q_{peak} produced from the Q_{CL} protocol is not meaningfully different from the Q_{step} protocol using a non-inferiority design.

Secondary objectives

(1) to determine the reliability of the Q_{CL} and Q_{step} protocols, (2) to determine whether the VO_2 and HR obtained from the two experimental protocols are not different from the $VO_{2\text{peak}}$ and HR_{peak} obtained from the baseline $VO_{2\text{peak}}$ test, and (3) to determine whether the VO_2 measured by the Innocor is lower than the metabolic cart.

Hypothesis

We hypothesize that the Q_{CL} protocol will produce a Q_{peak} that is not different (by a margin of noninferiority of 0.5 L/min) compared to the Q_{step} protocol. A Q_{peak} of 0.5 L/min was the TE in a previous study in our laboratory (9), and is therefore deemed to be the minimum meaningful difference for determinations of Q_{peak} .

Methods

Participants

Participants will be recruited from the McMaster community and surrounding area through printed posters, web-based advertisements, and word of mouth.

Inclusion criteria:

- Adults aged 18-35 years.
- Meeting the Canadian 24-hour Movement Guidelines for Adults for aerobic physical activity, i.e. ≥ 150 minutes of moderate to vigorous activity per week (13). This will be assessed using the Canadian Society for Exercise Physiology Get Active Questionnaire (GAQ) (14).

Exclusion criteria:

- Diagnosis of any cardiovascular, respiratory, or metabolic disease that would preclude participation from a clinical standpoint, as determined by answering ‘yes’ to any of the questions on the first page of the GAQ.

Details of the experimental protocol, purpose and potential risks of participation will be explained to all participants and written informed consent will be obtained prior to participation in the study. This study has been approved by the Hamilton Integrated Research Ethics Board (Project # 13339).

Sample size determination

A calculation performed using G*Power (v 3.1.9.2) for a two-tailed dependent means (matched pairs) t-test estimated that a sample size of 34 was required to detect a medium effect size ($d_z=0.5$) with 80% power at an alpha level of 0.05 (Figure 1). A medium effect size was deemed

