A two-tailed paired samples t-test will be performed to compare each of Q_{peak}, HR_{peak}, and W_{peak} between the two experimental conditions (Q_{CL} vs Q_{step}). A two-tailed paired samples t-test will be performed to compare each of VO_{2peak}, HR_{peak}, and W_{peak} between the baseline and verification VO_{2peak} tests, to compare Q_{peak} between the first and second Q_{CL} and Q_{step} tests, and to compare VO_{2peak} between the VO_{2peak} test and each of VO_{2CL} and VO_{2step}. Significance will be set to p<0.05. Effect sizes will be reported as Cohen's d_z and 95% confidence intervals (CI) will also be determined. Q_{peak} estimated by the Q_{CL} protocol will be considered noninferior to the Q_{step} protocol if the 95% CIs for the change in Q_{peak} fall within the margin of noninferiority (i.e., 0.5 L/min) (18, 19).

Reliability of each experimental protocol and of the VO_{2peak} tests will be calculated as the TE using the following formula (20):

$$TE = (SD_{diff} \div \sqrt{2} \div grand\ mean) \times 100$$

Where SD_{diff} is the standard deviation of the difference scores between the 2 measurements, and the grand mean is the mean of all measurements included in the analysis. The TE will be expressed as a percentage.

Perspectives and significance

IGR provides a noninvasive method for determining Q_{peak} , and assessing potential changes elicited by acute and chronic exercise interventions. The proposed work will systematically compare two methods for determining IGR-derived Q_{peak} , to assess potential differences between protocols as well as reliability of each method. This research will provide novel comparative data and inform decisions by researchers regarding choice of Q_{peak} protocol in future studies.

Strategies to reduce bias

Selection bias

The order of experimental trials will be randomized for each participant using Microsoft Excel by an investigator not involved in participant enrollment. This investigator will inform the other investigators of the trial order after baseline testing, and 24 hours before the first experimental trial for each participant. The investigator performing the randomization will play a secondary role in data collection.

Performance and detection bias

Given the distinct nature of each experiment, it is not possible to blind investigators or participants to the order of experimental trials. However, we will limit performance bias by blinding participants to the study hypotheses.

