Reporting bias

The current protocol, which clearly states the primary and secondary outcomes and hypotheses, will be published in an open access repository prior to participant recruitment.

Summary of analysis plan

| Question | Hypothesis | Data collection plan | Analysis plan | Interpretation |
|---|--|---|--|--|
| Is Q_{peak} determined by Q_{CL} noninferior to Q_{step} ? | Q_{CL} is noninferior to Q_{step} . | Measure Q_{peak} following Q_{CL} and Q_{step} using a randomized within-subject design. | Calculate 95% CIs for the mean difference in Q_{peak} between Q_{CL} and Q_{step} . | Q_{CL} is noninferior to Q_{step} if the lower bound of the CI is within 0.5 L/min. |
| What is the reproducibility of the Q_{CL} and Q_{step} protocols? | Reproducibility will be similar between Q_{CL} and Q_{step} . | Measure Q_{peak} during 2 Q_{CL} tests and 2 Q_{step} tests in a randomized order. | Calculate the TE between 1) the 2 Q_{CL} tests, and 2) the 2 Q_{step} tests. | Result will provide an indication of Q_{peak} reproducibility. |
| Is the HR_{peak} different between Q_{CL} and Q_{step} ? | HR_{peak} will not be significantly different between Q_{CL} and Q_{step} . | Measure HR_{peak} during Q_{CL} and Q_{step} using a randomized within-subject design. | Perform a paired t-test for HR_{peak} between Q_{CL} and Q_{step} . | If HR_{peak} is not significantly different between Q_{CL} and Q_{step} , it suggests participants are similarly close to “max” values during both protocols. |
| What is the reproducibility of the $VO_{2\text{peak}}$ test? | The reproducibility for the $VO_{2\text{peak}}$ tests will be approximately 5%. | Measure $VO_{2\text{peak}}$ during the baseline and verification $VO_{2\text{peak}}$ tests. | Calculate the TE of the baseline and verification $VO_{2\text{peak}}$ tests. | Result will provide an indication of $VO_{2\text{peak}}$ test reproducibility. |

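### The summary table hypothesises similar reproducibility of the two protocols, but plans only one typical-error estimate for each, so that comparison can be neither supported nor refuted

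*Protocol*

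**What the plan says.** The first secondary objective (Protocol, Secondary objectives) is "to determine the reliability of the Q_{CL} and Q_{step} protocols". The Background gives a reason for it: "no study has assessed the reliability of the Q_{CL} and Q_{step} protocols for determining Q_{peak} within the same group of participants".

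The reproducibility row of the Summary of analysis plan fixes three things:

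- Hypothesis: "Reproducibility will be similar between Q_{CL} and Q_{step".
- Analysis: "Calculate the TE between 1) the 2 Q_{CL} tests, and 2) the 2 Q_{step} tests".
- Interpretation: "Result will provide an indication of Q_{peak} reproducibility".

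The Statistical analysis section adds the formula: "Reliability of each experimental protocol and of the VO_{2peak} tests will be calculated as the TE using the following formula (20". The formula divides the standard deviation of the difference scores by √2 and by the grand mean, and multiplies by 100. It yields one number per protocol. The 95% confidence intervals in that section appear in the preceding paragraph, with the paired t-tests and effect sizes.

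For earlier values, the Background says of the constant-load protocol "and the TE was 4.7% (9"), and puts step tests at about 7%.

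**The concern.** The hypothesis is about two protocols relative to each other, while the analysis and interpretation describe each one separately. Nothing planned measures how far apart the two TEs are, how uncertain that distance is, or how small it must be to count as similar. The paired t-tests of first against second test do not fill the gap: they look for a shift in the mean within a protocol, whereas TE is built from the spread of the differences.

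Other rows of the same table are complete in this respect. The noninferiority rows each give a confidence interval and a margin (0.5 or 0.2 L/min), and the heart-rate row gives a test.

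At stake is how the two TEs would be read in the report. The protocol says its results should help researchers choose between protocols. With no interval on the contrast, a chance gap could pass for an advantage of one protocol, and a real gap could pass for similarity.

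**Working it through.** **Inputs.** From the protocol: n = 34 (Sample size determination); TE = SD_diff ÷ √2 ÷ grand mean × 100 (Statistical analysis); earlier TEs of 4.7% and about 7% (Background). Assumed here: 34 participants complete both repeats of both protocols, difference scores are normal and independent between protocols, and the grand mean is fixed.

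**The plan's own figure.** For a two-tailed paired t-test with d_z = 0.5 and alpha 0.05, exact noncentral-t power is 0.795 at n = 33 and 0.808 at n = 34. The stated 34 reproduces. It was set for a difference in mean Q_peak, not for TE.

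**Precision of one TE.** With the grand mean fixed, TE is proportional to an SD on 33 degrees of freedom. The 95% limits are TE × √(33/χ²).

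- Lower factor: √(33/50.73) = 0.81.
- Upper factor: √(33/19.05) = 1.32.
- An observed 4.7% has an interval of 3.8% to 6.2%; an observed 7.0% has 5.6% to 9.2%.

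**Precision of a ratio of two TEs.** The 95% limits are ratio ÷ √F and ratio × √F, where F is the 97.5% point of F(33,33) = 2.002 and √F = 1.415.

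- Factors: 1/1.415 = 0.71 and 1.42.
- For example, 6.5% against 4.7% is a ratio of 1.38, with limits 1.38/1.415 = 0.98 and 1.38 × 1.415 = 1.96. That is compatible with equality and with nearly a doubling.

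**Allowing for the same participants.** The Pitman-Morgan limits at an observed ratio of 1 are the square roots of K ± √(K² − 1), with K = 1 + 2t²(1 − r²)/32, t = 2.037, and r the correlation between the two sets of difference scores. At an assumed r = 0.5, K = 1.194 and the factors are 0.74 and 1.36. Pairing helps only modestly.

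**What two bare TEs would show.** Take a band of 0.8 to 1.25 for the observed ratio. The band is illustrative; the protocol gives none. From F(33,33), with independent difference scores:

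| True ratio | Observed ratio inside 0.8–1.25 |
|---|---|
| 1.00 | 79% (outside: 21%) |
| 1.30 (assumed) | 41% |
| 7.0/4.7 = 1.49 | 16% |

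**Power for the contrast.** A two-sided 5% test of a true ratio of 1.49 has about 61% power with uncorrelated difference scores, 65% at an assumed correlation of 0.3, and 74% at 0.5. In the uncorrelated case, 80% power needs a ratio of about 1.64.

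**Could similarity be confirmed?** At the most favourable observed ratio, exactly 1, the 95% interval is 0.71 to 1.42, or 0.74 to 1.36 with r = 0.5. Neither fits inside 0.8 to 1.25. By the formula above, fitting would need r of about 0.78.

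**The case against.** The strongest reply is that this part of the study is estimation throughout. The objective is to determine reliability, the outcome list refers to reproducibility for each protocol, the question in the table row asks what the reproducibility is, and the interpretation cell promises only an indication. Two TEs satisfy all of that, and where the authors want a decision they give an interval and a margin. This stands for the objective. It does not remove the hypothesis cell, which makes a between-protocol claim that the rest of its row does not address.

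A second reply is that an interval on each TE is a detail that a statistical analysis plan commonly supplies, and that the general sentence on confidence intervals does not exclude TE. That is fair for the single TEs. But the protocol itself fixes hypothesis, analysis and interpretation for this question, and an interval on each TE would still leave no contrast and no criterion.

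Three stronger readings are tempting and unsupported:

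- A reader might infer that the study sets out to select the more reliable protocol. It says only that its results will inform researchers' choice.
- A reader might take 4.7% and about 7% as already showing different reliability. They come from different studies whose sizes the protocol does not give, so this cannot be judged from the document.
- A reader might infer that the authors will declare similarity by eye. No passage commits them to any declaration.

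**Conclusion.** The mismatch is real and confined to one secondary hypothesis. The planned analysis delivers the two reliability estimates but gives no basis for supporting or refuting their similarity. It would be wrong to conclude that the reliability objective as a whole goes unanswered.

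In size, a ratio of two TEs is uncertain by a factor of about 1.4 in either direction at n = 34. This rests on complete repeat data, normal and independent difference scores, and a fixed grand mean; a correlation of 0.5 between the two sets of differences would narrow the factor to about 1.36. The shares falling inside or outside 0.8 to 1.25 depend also on that illustrative band. The primary noninferiority comparison is untouched.

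**What to change.** In the Statistical analysis section and the reproducibility row of the table:

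1. Report each TE with a 95% confidence interval.
2. Report the ratio of the constant-load TE to the step TE with a 95% interval from a bootstrap that resamples participants and recomputes both TEs each time. This respects the pairing and the scaling by the grand mean. Pitman-Morgan is an alternative only if each protocol's difference scores are first divided by that protocol's grand mean, because it compares SDs and not TEs.
3. Draw any comparative statement from the ratio interval, and state that an interval including 1 does not demonstrate similarity.
4. Choose one of two routes in advance. Either state a ratio margin that counts as similar, accepting that a narrow one such as 0.8 to 1.25 (illustrative) generally cannot be confirmed with 34 participants, or reword the hypothesis as descriptive. Rewording is the simpler route.

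The cost is a few lines of analysis on data already to be collected, with no added visits. The price is a less firm conclusion about relative reliability.
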